3.8 Isotopic bone scan

Bone lesions identified on an isotopic bone scan at baseline and confirmed by CT, MRI or X-ray at baseline should be recorded as NTLs and followed by the same method as per baseline assessment.

Isotopic bone scans may be used as a method of assessment to identify the presence of new bone lesions at follow-up visits. New lesions will be recorded where a positive hot-spot that was not present on the baseline bone scan assessment is identified on a bone scan performed at any time during the study. The Investigator should consider the positive hot-spot to be a significant new site of malignant disease and represent true disease progression in order to record the new lesion. Confirmation by CT, MRI and x-ray is recommended where bone scan findings are equivocal.

3.9 FDG-PET scan

FDG-PET (fluorodeoxyglucose positron emission tomography) scans may be used as a method for identifying new lesions, according with the following algorithm: New lesions will be recorded where there is positive FDG uptake (defined as when an uptake greater than twice that of the surrounding tissue is observed) not present on baseline FDG-PET scan or in a location corresponding to a new lesion on CT/MRI at the same follow-up visit. If there is no baseline FDG-PET scan available, and no evidence of new lesions on CT/MRI scans then follow-up CT/MRI assessments should be continued, scheduled as per protocol or clinical indicated, in order to confirm new lesions.

4. TUMOUR RESPONSE EVALUATION

4.1 Schedule of evaluation

CT examinations of the chest and abdomen (including liver adrenal glands) will be used to assess tumour burden at baseline and follow-up visits. CT examination with intravenous contrast media administration is the preferred method. MRI should be used where CT is not feasible or it is medically contra-indicated.

Baseline tumour assessments should encompass all areas of known predilection for metastases in the disease under evaluation and should additionally investigate areas that may be involved based on signs and symptoms of individual patients and should be performed no more than 28 days before the start of study treatment. CT/MRI scan of the brain should be performed in patients with known or suspected brain metastases. Follow-up assessments should be performed every 6 weeks (± 7 days) after the start of treatment until discontinuation of study

treatment or withdrawal of consent. Any other sites at which new disease is suspected should also be adequately imaged at follow-up.

If an unscheduled assessment was performed and the patient has not progressed, every attempt should be made to perform the subsequent assessments as their scheduled visits. This schedule is to be followed in order to minimise any unintentional bias caused by some patients being assessed at different frequency than other patients.

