3.6.1 Procedures for discontinuation of a subject from investigational product

At any time, subjects are free to discontinue investigational product or withdraw from the study (ie, investigational product and assessments – see Section 3.7), without prejudice to further treatment. A subject that decides to discontinue investigational product will always be asked about the reason(s) and the presence of any adverse events. If possible, they will be seen and assessed by an Investigator(s). Adverse events will be followed up (See Section 6); and all study drugs should be returned by the subject.

Any subject who discontinues study treatment for reasons other than objective disease progression should have tumour assessments performed as scheduled in the protocol (See Table 1 and Table 2) until objective disease progression is documented or death occurs, unless consent is withdrawn. Study procedures related to PROs, SAEs and anti-cancer treatment must be captured until the subject no longer has RECIST 1.1 assessments (disease progression or permanent withdrawal from the study).

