4.3.3 Progression follow-up

Patients who discontinue AZD9291 for reasons other than progression will continue RECIST 1.1 assessments every 6 weeks (relative to first dose of AZD9291) for objective progression prior to RECIST modules freeze time (24 months post LSFD). The last tumour assessment data at 24 months post LSFD should be entered into RAVE per eCRF entering guidance. In addition to RECIST 1.1 assessments, the following assessments are also required during this follow-up period as detailed in the Study Plan (see [Table 1](#)):

Prior to RECIST modules freeze time:

- EORTC QLQ-C30 and EQ-5D-5L every 6 weeks and at the time of progression.
- EORTC QLQ LC13 and PRO-CTCAE every 3 weeks and at the time of progression.
- Plasma for ctDNA collected every 6 weeks up to and including progression (corresponding with the RECIST 1.1 assessments – and continuing after treatment discontinuation if this is in absence of progression)
- Adverse event collection detailed in [Table 6](#)
- Anti-cancer therapy collected every 6 weeks.

Change after RECIST modules freeze time:

- After RECIST modules freeze time, the sites will continue to perform tumour investigator's assessments every 12 weeks according to their local practice, both central imaging scans and investigator assessment data will not be collected into eCRF. Please refer to [Table 2](#).
- Plasma for ctDNA collected every 12 weeks up to and including progression (corresponding with the RECIST 1.1 assessments – and continuing after treatment discontinuation if this is in absence of progression). Please refer to [Table 2](#).

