PFS is defined as the time from enrolment until the date of objective disease progression or death (by any cause in the absence of progression) regardless of whether the patient withdraws from study therapy or receives another anti-cancer therapy prior to progression. Patients who have not progressed or died at the time of analysis will be censored at the time of the latest date of assessment from their last evaluable RECIST assessment.

However, if the patient progresses or dies after three or more missed RECIST assessments visits, the patient will be censored at the time of the latest evaluable RECIST assessment. If the patient has no evaluable visits or does not have baseline data they will be censored at 0 days unless they die within two visits of baseline.

The PFS time will always be derived based on scan/assessment dates not visit dates.

RECIST assessments/scans contributing towards a particular visit may be performed on different dates. The following rules will be applied

- Date of progression will be determined based on the earliest of the dates of the component that triggered the progression
- When censoring a patient for PFS the patient will be censored at the latest of the dates contributing to a particular overall visit assessment

Overall Survival

Overall survival is defined as the time from the date of first dose until death due to any cause. Any patient not known to have died at the time of analysis will be censored based on the last recorded date on which the patient was known to be alive.

Note: Patients should be contacted in the 2 weeks following the data cut-off for the final survival analyses to provide complete survival data

HRQoL & Symptoms

Patient reported outcomes will be assessed using the EORTC QLQ-C30 and QLQ LC13 questionnaires. The QLQ-C30 consists of 30 questions which can be combined to produce 5

functional scales (Physical, Role, Cognitive, Emotional, Social), 3 symptom scales (Fatigue, Pain, Nausea/vomiting), 5 individual items (dyspnoea, insomnia, appetite loss, constipation, diarrhoea) and a global measure of health status. The QLQ LC13 is a lung cancer specific module comprising 13 questions to assess lung cancer symptoms (cough, haemoptysis, dyspnoea and site-specific pain), treatment related side-effects (sore mouth, dysphagia, peripheral neuropathy and alopecia) and pain medication. With the exception of a multi-item scale for dyspnoea, all are single items.

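### Appendix C 4.1 ends RECIST scans when treatment stops, contradicting Sections 3.6.1, 4.3.3 and 5.1.1; at any site that follows it, PFS and DoR could be informatively censored

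*Protocol*

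**What the plan says.** Appendix C, Section 4.1, sets the scan schedule: "Follow-up assessments should be performed every 6 weeks (± 7 days) after the start of treatment until discontinuation of study" "treatment or withdrawal of consent" (one sentence, broken by a page). Progression is not named as an end-point.

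The body of the protocol gives a different end-point:

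- Section 3.6.1: "Any subject who discontinues study treatment for reasons other than objective disease progression should have tumour assessments performed as scheduled in the protocol", and this continues "until objective disease progression is documented or death occurs, unless consent is withdrawn".
- Section 4.3.3: "Patients who discontinue AZD9291 for reasons other than progression will continue RECIST 1.1 assessments every 6 weeks", up to the RECIST modules freeze 24 months after the last subject's first dose.
- Section 5.1.1 and Table 1: scans every 6 weeks, relative to first dose, until progression.

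Appendix C, Section 4.5, also requires scans to objective progression, but only for patients who stop because of symptomatic deterioration.

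Section 8.4 counts PFS events "regardless of whether the patient withdraws from study therapy or receives another anti-cancer therapy prior to progression". A patient without an event is censored at the last evaluable RECIST assessment, and a progression or death after three or more missed assessments is also censored there. DoR ends at the PFS event date, or at the PFS censoring time if there is no progression.

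**The concern.** For a patient who stops drug without progression, one current instruction ends imaging and another continues it. Such stops are foreseeable: Section 3.6 lists subject decision, adverse event, pregnancy, non-compliance and incorrect initiation, and Section 6.7 makes discontinuation permanent for certain toxicities. Appendix C 4.5 does not cover these cases.

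If a site works from Appendix C 4.1, later radiological progression goes unseen and the patient is censored close to the time of stopping. The defined estimand (progression regardless of treatment withdrawal) then drifts towards a while-on-treatment quantity. The investigator-based sensitivity analysis in Section 8.7.5 reads the same scans as the central review, so it could not reveal the gap. Scans not taken cannot be recovered at analysis.

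**Working it through.** The protocol states no figure to reproduce here. The check is a comparison of texts, followed by an illustration of size.

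**Texts side by side, for a patient who stops drug before progression**

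| Place | Scans end at |
|---|---|
| Appendix C 4.1 | treatment discontinuation or withdrawal of consent |
| Section 3.6.1 | progression or death, unless consent is withdrawn |
| Section 4.3.3 | progression (6-weekly up to the RECIST freeze) |
| Section 5.1.1, Table 1 | progression |
| Appendix C 4.5 (symptomatic deterioration only) | progression |

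The Appendix C 4.1 wording also departs from the body in the other direction. For a patient treated beyond progression it would keep scans going, whereas Section 4.2 excludes study RECIST assessments after progression.

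**Tracing the rules.** Under Appendix C 4.1 such a patient has no scan after stopping. Under Section 8.4 the PFS time is then the last evaluable scan date, censored, unless death occurs before three assessments have been missed. The same censoring time passes to DoR.

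**Size, on assumed inputs.** None of these inputs comes from the protocol: exponential times; on-treatment median PFS 10 months; a share *f* of 5%, 10% or 15% stopping before progression (175 × *f* ≈ 9, 18 or 26 patients); progression hazard after stopping *h* = 1, 2 or 3 times the on-treatment hazard; every site following Appendix C 4.1. The 6-week scan grid and deaths are ignored.

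- On-treatment hazard λ = ln 2 / 10 = 0.0693 per month.
- Stopping hazard μ = λ*f*/(1 − *f*), so that a share *f* stops first.
- With scans stopped at discontinuation, Kaplan–Meier estimates exp(−λ*t*): median 10.0 months, and exp(−0.0693 × 12) = 43.5% at 12 months.
- With scans continued, writing *a* = λ + μ, S(*t*) = e^(−*at*) + [μ/(*a* − *h*λ)] × [e^(−*h*λ*t*) − e^(−*at*)].

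Worked case, *f* = 15%, *h* = 3: μ = 0.0693 × 0.15/0.85 = 0.0122, *a* = 0.0815, *h*λ = 0.2079. At *t* = 9.29, S = 0.469 + (−0.0968)(0.145 − 0.469) = 0.500, so the median with full follow-up is 9.29 months.

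| Stopping before progression | *h* | Median, full follow-up (months) | Overstatement of median (months) | Overstatement at 12 months (points) |
|---|---|---|---|---|
| 5%, 10% or 15% | 1 | 10.00 | 0 | 0 |
| 5% | 2 | 9.86 | 0.14 | 0.6 |
| 5% | 3 | 9.77 | 0.23 | 1.0 |
| 10% | 2 | 9.71 | 0.29 | 1.3 |
| 10% | 3 | 9.53 | 0.47 | 2.0 |
| 15% | 2 | 9.56 | 0.44 | 1.9 |
| 15% | 3 | 9.29 | 0.71 | 3.1 |

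A simulation with more extreme assumptions (20% stopping, hazard 4 times as high) overstates the median by about 13%.

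**Against sampling error.** With 175 patients fully followed, the large-sample standard error of the median is 1/(2 × 0.0347 × √175) ≈ 1.1 months, where 0.0347 = λ/2 is the density at the median. The 95% interval is about ±2.1 months.

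**The case against.** The strongest reply is that the intended rule is plain. Sections 3.6.1, 4.3.3 and 5.1.1 and Table 1 all state it. Table 1 has its own progression follow-up column. Its plasma-sampling footnote, and that of Table 5, presuppose RECIST visits after discontinuation. Appendix C 4.5 defers to the protocol. Section 5.1.1 sends the reader to Appendix C for lesion and response definitions but to Section 4 for considerations related to the assessments. On this view a lone appendix sentence misleads few sites.

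Most of this stands, and it limits the expected harm. It does not remove the conflict. No clause says which text prevails: the only precedence rule, in Section 9.2.2, concerns the Clinical Study Agreement. Appendix C also presents itself as containing study-specific requirements, and Section 4.1 asks for its own schedule to be followed to avoid bias.

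Two further objections stand. The PFS definition fixes which events count and does not itself order scans; the orders are in the sections listed above. The affected patients are not wholly lost either, since they contribute follow-up to their last scan and an early death still counts as an event.

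A reader might infer that PFS and DoR will be biased upward. The documents do not support that. It needs sites to follow this sentence against the rest of the protocol, and it needs stopping to be related to progression risk; with equal hazards the bias is zero.

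**Conclusion.** The inconsistency is real and in current text, and it should be fixed. The design itself, follow-up to progression regardless of treatment, is sound and stated repeatedly; one appendix sentence contradicts it.

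The consequence is conditional: PFS and DoR could be informatively censored at any site that applies Appendix C 4.1. On the assumptions shown, median PFS is overstated by about 0 to 0.7 months and the 12-month rate by about 0 to 3 points. These are upper-end figures in that every site is assumed to follow the appendix, and the whole range lies inside the sampling error of the median.

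A reader might also infer a threat to the primary endpoint. That is not supported: ORR needs a response confirmed at least 4 weeks later, so the exposed case is a patient whose confirmation scan would fall after drug stop. The reason to act is that missed scans are irrecoverable and the correction is cheap.

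**What to change.** Reconcile the Appendix C 4.1 sentence with Sections 3.6.1, 4.3.3 and 5.1.1, so that endpoint imaging is collected until objective progression (or the RECIST modules freeze, death or withdrawal of consent) whether or not study treatment has stopped. Wording tied to progression would also remove the mismatch with Section 4.2 for patients treated beyond progression.

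The cost is one sentence in an appendix. It requires no scans beyond those the body already asks for and changes no treatment rule. If sites have already been working to the protocol, a short clarification to them would serve the same purpose for patients still in follow-up before the freeze.

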4.2 Target lesions

4.2.1 Documentation of target lesions

A maximum of 5 measurable lesions, with a maximum of 2 lesions per organ (including lymph nodes), representative of all lesions involved, should be identified as TLs at baseline. Target lesions should be selected on the basis of their size (longest diameter for non-nodal lesions or short axis for nodal lesions) but in addition should be those that lend themselves to reproducible repeated measurements. It may be the case that, on occasion, the largest lesion does not lend itself to reproducible measurement in which circumstance the next largest lesion, which can be measured reproducibly, should be selected.

The site and location of each TL should be documented as well as the longest diameter for non-nodal lesions (or short axis for lymph nodes). All measurements should be recorded in millimetres. At baseline, the sum of the diameters for all TLs will be calculated and reported as the baseline sum of diameters. At follow-up visits the sum of diameters for all TLs will be calculated and reported as the follow-up sum of diameters.

Special cases:

- For TLs measurable in 2 or 3 dimensions, always report the longest diameter. For pathological lymph nodes measurable in 2 or 3 dimensions, always report the short axis.
- If the CT/MRI slice thickness used is >5 mm, the minimum size of measurable disease at baseline should be twice the slice thickness of the baseline scan.
- If a lesion has completely disappeared, the longest diameter should be recorded as 0 mm.
- If a TL splits into two or more parts, then record the sum of the diameters of those parts
- If two or more TLs merge then the sum of the diameters of the combined lesion should be recorded for one of the lesions and 0 mm recorded for the other lesion(s)
- If a TL is believed to be present and is faintly seen but too small to measure, a default value of 5 mm should be assigned. If an accurate measure can be given, this should be recorded, even if it is below 5 mm.

- If a TL cannot be measured accurately due to it being too large, provide an estimate of the size of the lesion
- When a TL has had any intervention eg, radiotherapy, embolisation, surgery etc, during the study, the size of the TL should still be provided where possible

4.2.2 Evaluation of target lesions

Table 11 provides the definitions of the criteria used to determine objective tumour visit response for TLs.

Table 11 Overall Visit Response for Target Lesions

Complete Response (CR)	Disappearance of all TLs since baseline. Any pathological lymph nodes selected as TLs must have a reduction in short axis to <10 mm.
Partial Response (PR)	At least a 30% decrease in the sum of diameters of TLs, taking as reference the baseline sum of diameters.
Stable Disease (SD)	Neither sufficient shrinkage to qualify for PR nor sufficient increase to qualify for PD.
Progressive Disease (PD)	At least a 20% increase in the sum of diameters of TLs, taking as reference the smallest sum on study (this includes the baseline sum if that is the smallest on study). In addition to the relative increase of 20%, the sum must also demonstrate an absolute increase of at least 5 mm.
Not Evaluable (NE)	Only relevant if any of the TLs were not assessed or not evaluable or had a lesion intervention at this visit. Note: If the sum of diameters meets the progressive disease criteria, progressive disease overrides not evaluable as a TL response

4.3 Non-Target lesions

4.3.1 Evaluation of non-target lesions

All other lesions (or sites of disease) not recorded as TLs should be identified as NTLs at baseline. Measurements are not required for these lesions but their status should be followed at subsequent visits. At each visit, an overall assessment of the NTL response should be recorded by the investigator. Table 12 provides the definitions of the criteria used to determine and record overall response for NTLs at the investigational site at each visit.

Table 12 Overall Visit Response for Non-Target Lesions

Complete Response (CR)	Disappearance of all NTLs since baseline. All lymph nodes must be non-pathological in size (<10 mm short axis).
Non-CR/Non-PD	Persistence of one or more NTLs.
Progressive Disease (PD)	Unequivocal progression of existing NTLs. Unequivocal progression may be due to an important progression in one lesion only or in several lesions. In all cases the progression MUST clinically significant for the physician to consider changing or stopping therapy.
Not Evaluable (NE)	Only relevant when one or some of the NTLs were not assessed and in the investigator's opinion they are not able to provide an evaluable overall NTL assessment at this visit. Note: For patients without TLs at baseline, this is relevant if any of the NTLs were not assessed at this visit and the progression criteria have not been met.

To achieve 'unequivocal progression' on the basis of NTLs, there must be an overall level of substantial worsening in non-target disease such that, even in presence of SD or PR in TLs, the overall tumour burden has increased sufficiently to merit discontinuation of therapy. A modest 'increase' in the size of one or more NTLs is usually not sufficient to qualify for unequivocal progression status.

4.4 New Lesions

Details of any new lesions will also be recorded with the date of assessment. The presence of one or more new lesions is assessed as progression.

A lesion identified at a follow up assessment in an anatomical location that was not scanned at baseline is considered a new lesion and will indicate disease progression.

The finding of a new lesion should be unequivocal: ie, not attributable to differences in scanning technique, change in imaging modality or findings thought to represent something other than tumour.

If a new lesion is equivocal, for example because of its small size, the treatment and tumour assessments should be continued until the new lesion has been confirmed. If repeat scans confirm there is a new lesion, then the progression date should be declared using the date of the initial scan.

4.5 Symptomatic deterioration

Symptomatic deterioration is not a descriptor of an objective response: it is a reason for stopping study therapy.

Patients with ‘symptomatic deterioration’ requiring discontinuation of study treatment without objective evidence of disease progression at that time should continue to undergo RECIST 1.1 assessments according to the clinical study protocol until objective disease progression is observed.

4.6 Evaluation of Overall Visit Response

The overall visit response will be derived using the algorithm shown in [Table 13](#).

Table 13 Overall Visit Response

Target lesions	Non-Target lesions	New Lesions	Overall response
CR	CR	No	CR
CR	NA	No	CR
CR	Non-CR/Non PD	No	PR
CR	NE	No	PR
PR	Non PD or NE	No	PR
SD	Non PD or NE	No	SD
NA	Non CR/Non PD	No	SD (Non CR/non PD)
NE	Non-PD or NE	No	NE
NA	NE	No	NE
PD	Any	Yes or No	PD
Any	PD	Yes or No	PD
Any	Any	Yes	PD

CR=complete response, PR=partial response, SD=stable disease, PD=progressive disease
IR=incomplete response, NE=not evaluable, NA=not applicable (relevant when no NTLs at baseline)

5. SPECIFICATIONS FOR RADIOLOGICAL IMAGING

These notes are recommendations for use in clinical studies. The use of standardised protocols for CT and MRI allows comparability both within and between different studies, irrespective of where the examination has been undertaken.

